Statistical analysis will be undertaken using time series regression models. Pre-intervention and post-intervention (virtual and actual implementation) trends will be evaluated. In addition, the pre and post intervention effects at Sefton will be compared with national trends in order to further investigate the effects of possible secular trends. Analysis and reporting will be undertaken according to recommended quality criteria (Ramsay et al, 2003). The best fit pre intervention and post intervention lines will be estimated using linear regression and autocorrelation will be adjusted for by using the maximum likelihood methods where appropriate (Draper & Smith 1981). First order autocorrelations will be tested for statistically using the Durbin – Watson statistic and higher – order autocorrelations will be investigated using the autocorrelation and partial autocorrelation function.

Two effect sizes will be estimated. First, a change in level of outcome at the first point of after the introduction of the intervention will be estimated for each of the referral outcomes (Primary Care, Secondary care, DWSPI, rejected). This will be carried out by extrapolating the pre intervention regression line to the first post intervention point. The difference between this extrapolated point and the post intervention regression estimate for the same point will represent the estimated change in level of referrals. Secondly, a change in the slopes of regression lines will be investigated by calculating the post intervention minus pre intervention slope. The difference observed for each change will be further investigated for statistical significance.

Data will also be presented descriptively and graphically on the number and nature of referrals according to the referral destinations of rejected, primary care, primary advanced or secondary care.

Version 2 15 September 2015

Any trends observed for referrals to secondary care for Sefton will be compared with national trends using Hospital Episode Statistics (HES), which will be obtained via NHS Sefton and analysed for statistical significance at each recorded time point.

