The introduction of the 2006 dental contract provided a Band II payment for tooth extraction that, on North West averages, provides a fee of £75 for one or more teeth to be extracted within a single course of treatment. Figures from acute trusts and eReporting data suggest an exponential increase in referrals of MOS to secondary care. There are a number of reasons postulated for this including perverse incentives in the dental contract (GDPs receive payments for referrals alone at the same Band II level) and that younger dentists may have limited competency as undergraduate experience in MOS treatments is limited (MEE Report, 2010). A number of acute trusts in the North West have struggled to deliver capacity against this increase in demand and work has been undertaken to manage this through a number of routes and approaches.

Current demand management strategies for MOS – NHS Manchester

NHS Manchester has continued the early work started in NHS Trafford with the introduction of the hybrid referral management pilot. All referrals to secondary care are captured (either by post, email or fax) and then scanned for paper-based triage. A website provides practitioners with a live status check on their referral's progress. This work has taken place under the Dental QIPP programme stream in the North West for demand management. By producing an agreed proforma, requiring adherence to a minimum dataset (including provision of appropriate radiographs) and ensuring administrative procedures to check compliance, there has been a 9% reduction in referrals into all dental specialties as well as the diversion of considerable numbers of referrals into primary care and advanced primary care settings. It is important to recognize that, given the drive to decrease costs whilst improving quality of care across the NHS, referral management systems are developing rapidly.

NEED

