Patients referred for Minor Oral Surgery by participating sites Clinicians involved in referral and triage activities NHS commissioners NHS Acute trust managers

Inclusion / exclusion characteristics

Patients must:

- 1. Be referred for oral surgery
- 2. Be able to understand the patient information leaflet and be able to give informed consent
- 3. Adults aged > 18

IX. STUDY DESIGN

Interrupted time series design combined with qualitative analysis

Version 2 15 September 2015

Phase 1, preparative work and baseline data collection

Months 1-12

Baseline data collection: Referral data, SUS/ SLAM data/ practice questionnaires

Installation of new referral system and training

Phase 2, virtual implementation (implementation1)

Months 12-24

Sandbox (virtual) implementation of referral system (all referrals ultimately to secondary care, with monitoring of potential DWSpI & primary care cases)

Data collection: Referral data, SUS/ SLAM data Interviews with professionals AQP commissioning process Financial Assessment

Phase 3, full implementation (implementation 2) Months 24-36

Full implementation of eReferral system (system fully operational, with diversion to primary care settings)

Data collection: Referral data, SUS/ SLAM data

Interviews with service users (post implementation of referral management) Interviews with professionals (post implementation of referral management)

Economic evaluation

It is important that there is high precision in comparison of the methods of triage and that erroneous referrals should ideally to be sent to secondary care rather than primary care, to ensure patient safety and service quality. The sensitivity and specificity of the triage has consequently been assessed in a recent study (Research Ethics Committee approval: London Fulham, reference 12/LO/1912).

This study will address the impact of the introduction of the new eReferral system and will comprise two main components, which will be described in more detail below:

- 1. Interrupted time series study
- 2. Qualitative interviews with service users and clinicians and subsequent thematic analysis

Interrupted time series study

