This is a before and after methodological approach, which will involve collection of baseline data over 12 months, followed by staged implementation. Implementation will take place over two phases: a sandbox, or virtual implementation of the system (referral decisions made by GDPs will be captured, however all patients will ultimately be treated in secondary care) followed by full implementation of the system, (appropriately referred patients being treated in both primary and secondary care settings).

The pilot study suggests that changes in referral behaviour can be detected as early as three months following the introduction of a management system. The cost reductions seen by triage diversion are seen immediately. However, in order to understand the long-term implications of the referral system, including any reactive behaviour by GDPs or Secondary Care providers we are proposing to run the introduction of the system for 12 months and the full diversion service for a further 12 months. This should allow a full financial year's worth of cost data to be assessed as well as determining the degree of adaptation to the system. The time period will also enable a robust assessment of primary care treatment quality – i.e. there will be sufficient time to determine if cases treated in primary care return to secondary care for additional or remedial treatment as well as tracking seasonal variations in

Version 2 15 September 2015

referrals. For example we have noted decreases in referral volumes around December and January (relating to the holiday period) and increases in volumes round March (relating to end of financial year).

Implementation 1: Virtual Referral management without diversion (year 2)

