The quantitative analysis has been designed to evaluate the impact of a change in service, with the primary analysis using a piecewise regression / interrupted time series analysis (ITS) design. This is an appropriate methodology to evaluate the effects of a change in service delivery. Whilst it is acknowledged that the lack of a concurrent control group can be considered a weakness (Brown & Lilford, 2008), the nature of the investigation and implementation precludes such a design. The proposed study design and analysis will aim to minimize threats to internal validity (Ramsay et al, 2003): A single PCT boundary (NHS Sefton) with a diverse practice and patient profile has been identified for study; lengthy evaluation pre-intervention and during two stage implementation over three years will address any concerns regarding secular trends (Brown & Lilford, 2009). Additionally, trends observed in Sefton over the implementation period with be compared with national trends in oral surgery referrals through the examination of Hospital Episode Statistics (HES) data. This design will enable 24 months of referral management assessment during the study, and thus captures and enables the measurement of seasonal variations in referral patterns. Further, a large intervention effect has been observed in an earlier pilot study, with a re-direction of MOS referrals from secondary care to primary care based services of over 68% (data from Central Manchester Foundation Trust). The primary outcome measures will be the monthly reported number and ultimate destination of referrals from baseline through to six months, implementation stage 1 referral management alone (12 to 24 months) and Implementation stage 2, referral management with diversion (24 to 36 months). Analysing monthly data has a number of advantages: it enables the cyclical nature of referrals observed in the pilot study to be accounted for; will illustrate whether referral management alone (the process of collecting, assessing and administratively triaging referrals in the absence of diversion) results in a decrease in referrals into secondary care; short-term changes will not be missed; any observed effect is maintained or return returns to original levels. The principal analysis will be to determine whether the implementation of the Referral Management System with diversion has an effect that is significantly different from any underlying secular trend.

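### Installation and training are undated within the baseline phase and the baseline window is stated in two ways, so the extrapolated pre-intervention line is open to bias of unknown size and sign

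*Protocol*

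**What the plan says.** Section IX of the Protocol titles its first phase "Phase 1, preparative work and baseline data collection" and places it in months 1-12. Two activities are listed there: "Baseline data collection: Referral data, SUS/ SLAM data/ practice questionnaires" and "Installation of new referral system and training". It does not say in which month either installation or training happens, who is trained, or on what.

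The baseline window is given twice:

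- Section IX, Interrupted time series study, describes "collection of baseline data over 12 months, followed by staged implementation".
- Section XI, Quantitative data analysis, gives the windows of the monthly primary outcome as "from baseline through to six months, implementation stage 1 referral management alone (12 to 24 months", and then stage 2 at 24 to 36 months. On that wording months 7-12 belong to no segment.

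On the level change, Section XI says: "This will be carried out by extrapolating the pre intervention regression line to the first post intervention point". The second effect size is the post-intervention slope minus the pre-intervention slope. Nothing in the Protocol removes training months from the line, defines a transition period, or takes Sefton counts from before month 1.

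**The concern.** An interrupted time series without a concurrent control uses its pre-intervention line as the counterfactual. Here that line may be fitted through months in which the system is being installed and people are being trained to use it. The intervention acts on referrer behaviour. Section IX itself says that collecting and administratively triaging referrals can lower them without any diversion, and it expects dentists and hospitals to react to the system. Some change before the formal start is therefore possible.

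If that happens, the line no longer describes the undisturbed series. The level change is measured from the wrong point and the slope change from the wrong slope. For example, a lasting fall late in the baseline tilts the line downwards. The reduction then looks too small, and the slope change can look like an effect wearing off.

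The exposure is to total and secondary-care referral counts. System rejection and diversion do not operate in Phase 1.

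**Working it through.** The Protocol states no numerical level change, so there is no figure to reproduce. The check applies the Section XI rule to the two stated baseline windows.

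**Inputs.** Baseline months 1-12 (Section IX) or 1-6 (Section XI). The first post-intervention point is taken as month 13; the Protocol lists Phase 1 as months 1-12 and Phase 2 as months 12-24, so this is an assumption. The size and timing of any disturbance are also assumed.

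**Formula.** For a least-squares line through n months with mean m and sum of squares S, month t has weight 1/n + (13 − m)(t − m)/S on the value extrapolated to month 13. The error in the level change is minus the sum of weight × disturbance. The error in the pre-intervention slope is the sum of (t − m)/S × disturbance.

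**12-month line.** n = 12, m = 6.5, S = 143. The weights for months 1 to 12 are −0.167, −0.121, −0.076, −0.030, 0.015, 0.061, 0.106, 0.152, 0.197, 0.242, 0.288 and 0.333. Late months pull hardest.

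- Sum over months 7-12: 1.32. Sum over months 10-12: 0.86. Sum over months 4-12: 1.36.
- Sum over months 1-3: −0.36. Sum over months 4-6: 0.05.

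The table assumes a true level change of −20 a month against the undisturbed series and a disturbance of 5 a month.

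| Disturbance in baseline | Estimated level change | Error in pre-slope, per month |
|---|---|---|
| Lasting fall from month 4 | −20 + 5 × 1.36 = −13.2 | −0.47 |
| Lasting fall from month 7 | −20 + 5 × 1.32 = −13.4 | −5 × 18/143 = −0.63 |
| Lasting fall from month 10 | −20 + 5 × 0.86 = −15.7 | −5 × 13.5/143 = −0.47 |
| Temporary fall, months 1-3 | −20 − 5 × 0.36 = −21.8 | +0.47 |
| Temporary fall, months 4-6 | −19.8 | +0.16 |
| Rise, months 10-12 | −20 − 5 × 0.86 = −24.3 | +0.47 |

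The slope change carries the pre-slope error with opposite sign. A fall phased in linearly does less harm than an abrupt one. Reaching its full size over months 7-12 it costs 0.90 per unit, since (0.106×1 + 0.152×2 + 0.197×3 + 0.242×4 + 0.288×5 + 0.333×6)/6 = 0.90. Over months 10-12 it costs 0.61, since (0.242×1 + 0.288×2 + 0.333×3)/3 = 0.61.

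**Six-month line.** n = 6, m = 3.5, S = 17.5. Anything that starts in month 7 or later leaves the line untouched, and the estimate stays at −20.0. A lasting fall from month 4 has summed weight 0.438 + 0.981 + 1.524 = 2.94, giving −20 + 5 × 2.94 = −5.3.

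**Precision.** With independent errors of standard deviation sigma, the standard error of the extrapolated point is sqrt(1/n + (13 − m)²/S) × sigma.

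- Months 1-12: sqrt(1/12 + 6.5²/143) = 0.62 sigma.
- Months 1-6: sqrt(1/6 + 9.5²/17.5) = 2.31 sigma.
- Months 1-6 plus 24 earlier months (an assumed extension; n = 30, m = −8.5, S = 30 × 899/12 = 2,247.5): sqrt(1/30 + 21.5²/2,247.5) = 0.49 sigma.

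Simply dropping months 7-12 is therefore expensive. Dropping them and extending backwards is not, provided a straight line holds over the longer series.

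**The case against.** A reader might infer that the baseline is already affected. The Protocol does not support that. Dentists first use the system in Implementation 1 (year 2), and Section IX, Screening and Selection of Subjects, has referrals processed through it only during implementations 1 and 2. The pilot's behaviour change is dated from the introduction of a management system, not from training. No effect of installation or training is reported, and the content of the training is not described. This objection stands: contamination is a possibility, not a finding.

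A reader might also infer that the level change must be understated. That fails too. The table shows errors in both directions, depending on timing, direction and persistence.

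On the six-month window in Section XI, training confined to months 7-12 would not touch the line. That is correct, but no text confines it to those months. The same window more than doubles the error from a lasting fall that starts in month 4 (2.94 against 1.36 per unit), and its extrapolation is far less precise.

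The comparison with national Hospital Episode Statistics and the planned graphs are partial safeguards. They might reveal a local dip before the start, but they do not correct the Sefton line. Section XI's principal analysis concerns the system with diversion, from month 24, and does not say which earlier period supplies its pre-intervention line. Exposure of that contrast is therefore not established.

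Excluding transition months could be handled in an analysis plan that is not shown. The undated overlap and the two baseline windows, however, are in the Protocol itself.

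**Conclusion.** The point holds as a conditional one. Baseline collection shares months 1-12 with undated installation and training, the line from that phase is extrapolated as the counterfactual, and its length is stated inconsistently. If behaviour shifts before the start, the level and slope changes in total and secondary-care counts are biased.

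With a 12-month line, an abrupt lasting fall understates the reduction by 1.32 per unit if it starts in month 7 and 0.86 if it starts in month 10. A temporary fall in months 1-3 overstates it by 0.36 per unit, and a rise in months 10-12 by 0.86. These multipliers follow from the stated estimator with month 13 as the first post-intervention point. The disturbances themselves are assumptions, and the Protocol fixes neither their size nor their sign. The documents support neither a claim that the line is already distorted nor a claim that the effect is necessarily understated.

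The change is worth making because the series has no concurrent control and the protection is cheap.

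**What to change.** 1. Reconcile the baseline window between Section IX (12 months) and Section XI (six months), and say where months 7-12 belong.
2. Record the month in which installation and training first take place, by practice where possible.
3. Where monthly Sefton counts are available, extend the pre-intervention series to before month 1 from sources the Protocol already names: hospital referral receipt, SUS/SLAM and NHS Business Services Authority reporting. Section I cites earlier acute-trust and eReporting figures, which suggests that history may exist but does not show that monthly Sefton counts do.
4. Treat first training to system start as a transition period outside the pre-intervention line. At minimum, report a sensitivity analysis that excludes those months.

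The cost is a retrospective data extract and some rewording of Sections IX and XI. Older data may be coded differently, which should be checked before they are joined to the study series. The fit of a straight line over the longer period also needs checking, because Section I says: "Figures from acute trusts and eReporting data suggest an exponential increase in referrals of MOS to secondary care".

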PROTOCOL COVER SHEET

STUDY TITLE: An evaluation of an eReferral Management & Triage System for Minor

Oral Surgery Referrals from Primary Care Dentist

INVESTIGATOR: [name]

Professor of Dental Health,

The University of Manchester School of Dentistry

Dental Health Unit, [name]

[name]

STUDY PHASE: Effectiveness, implementation and impact

OBJECTIVES: To assess the effectiveness, implementation and impact of eReferral

management and triage for minor oral surgery

PARTICIPANTS: i) Female and male adults referred from primary dental care

practitioner for Minor Oral surgery

ii) Dentists working in primary and secondary careiii) Commissioners and NHS secondary care managers

STRUCTURE: Mixed methods: Interrupted time series design combined with

qualitative analysis

NUMBER OF CENTRES: 1 (NHS Sefton)

PRIMARY OUTCOME: Number and ultimate destination of referrals made by General Dental

Practitioners for MOS

SAMPLE: A census approach will be taken: All primary care dental practices and

secondary care hospitals within NHS Sefton/ will be incorporated into

the study. Purposive sampling will be used to select a smaller

qualitative sub-sample.

ESTIMATED TOTAL SAMPLE SIZE:

ADVERSE REACTIONS: N/A

STUDY ORIGINATORS: [name]

Protocol SDO-002-[name] 15 September 2015

Version 2

PAGE

PROTOCOL COVER SHEET	1
TABLE OF CONTENTS	1
I. INTRODUCTION	
II. AIMS	
III. STUDY DESIGN	
IV. INVESTIGATORS	
V. APPROVAL OF THE PROTOCOL	
VI. DURATION OF STUDY	
VII. SUBJECTS.	
IX. STUDY DESIGN	
XI. DATA ANALYSES	

Version 2 15 September 2015

An evaluation of an eReferral Management & Triage System for Minor Oral Surgery Referrals from Primary Care Dentists: Diagnostic Test Accuracy

I. INTRODUCTION

BACKGROUND

Minor Oral Surgery (MOS) referrals represent the largest volume, and cost, of referrals from primary dental care to secondary care. MOS referrals, in the main, involve the extraction of teeth and these treatments may be supplemented by adjunct IV sedation offerings. Care is typically provided in oral surgery units within acute hospitals and is consultant led with trainees of various levels undertaking the procedures. The average cost of an MOS referral to acute trusts in the North West region is circa £650. In the North West the total charge for MOS referrals in 2009/10 was £53,864,857.

Referrals from Primary Care General Dental Practitioners (GDPs)

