In addition to the primary outcome additional metrics will be provided based on the assessment of patient demographics (age, and IMD score), practice profile and treatment type. These data will provide a rich picture of the likely predictive variables involved in service diversion and will assist in service planning in the future. For example commissioning bodies can use these data, matched to a health needs assessment, to plan the level of primary care provision required. They may also be used to assist in administrative triage to reduce the burden on clinical triagers.

Cost effectiveness

In order to estimate the incremental costs (i.e. the net costs incurred by implementing the management and triage programme) costs will be calculated from the perspective of the commissioning body based on banded treatment costs for primary care services (including the MOS primary care service) and actual fees for secondary care (based on tariff charges for new patient assessment, follow on appointments and treatment complexity). In addition the cost of the management/triage programme, and any redirected referrals will be calculated based on primary data collection on the labour, capital and consumables used by the programme. Total costs and mean cost per patient will be compared across each implementation of the system from baseline, through implementation one and two. Costs will include any costs associated with care arising from treatment failures arising during a one-month period post treatment (such failures tend to be acute and hence a 4 week period is sufficient to detect these). The difference in total costs between baseline and implementation 1 and 2 will be used to

Version 2 15 September 2015

calculate a mean cost per referral avoided based on the programme's objective of avoiding unnecessary referrals. Costs to patients and patient carers will also be calculated using data collected by questionnaire on costs incurred in travelling to and from, and waiting and being treated at treatment facilities. These costs will include both the opportunity of cost of time as well as out of pocket costs for public transport costs or private transport, parking etc. Incremental patient costs will be combined with incremental service costs to provide a proxy for societal costs.

Qualitative element

How does remote centralised referral management (RCRM) impact on GDP referral behaviour and practice?

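### The cost per referral avoided rests on an unadjusted difference from the baseline year, although the protocol describes steeply rising referrals, and the patient-cost increment added to it starts from a later year

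*Protocol*

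**What the plan says.** The protocol's Cost effectiveness section compares total costs and mean cost per patient across baseline, implementation 1 and implementation 2. It then fixes the economic ratio: "The difference in total costs between baseline and implementation 1 and 2 will be used to" "calculate a mean cost per referral avoided based on the programme's objective of avoiding unnecessary referrals". It does not say how an avoided referral is counted, and it projects no expected cost or volume.

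The Introduction reports that acute trust and eReporting figures "suggest an exponential increase in referrals of MOS to secondary care". The Quantitative data analysis section responds to such a trend for referral outcomes: it fits pre- and post-intervention lines, extrapolates the pre-intervention line, and compares Sefton with national Hospital Episode Statistics (HES). None of this is extended to costs.

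On patient costs, the Phase 1 list for months 1-12 reads "Baseline data collection: Referral data, SUS/ SLAM data/ practice questionnaires". The section on the impact on patients sets the baseline for satisfaction and cost by postal questionnaire in implementation 1. The Cost effectiveness section then says: "Incremental patient costs will be combined with incremental service costs to provide a proxy for societal costs".

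**The concern.** If referrals would have grown without the system, the year 1 total is not what years 2 and 3 would have cost. The raw difference mixes the programme's saving with the cost of growth, and the two pull in opposite directions. A programme that works could be reported as saving little or nothing. The study is meant to weigh cost reduction against quality and training, so commissioners would be reading a distorted figure.

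The societal figure has a separate problem. The service increment is measured from year 1, before the system exists. The only patient-cost baseline is in year 2, when the system is already running and returning referrals below threshold. Adding the two gives a sum that describes neither comparison.

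**Working it through.** The protocol gives no figure for the cost per referral avoided, so there is nothing to reproduce. The check is arithmetic per 1,000 baseline referrals.

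**Inputs from the protocol**
- Secondary care cost, Background: "The average cost of an MOS referral to acute trusts in the North West region is circa £650".
- Effect of referral management alone, from the NHS Manchester pilot: "there has been a 9% reduction in referrals into all dental specialties".
- Diversion: 68% redirected, from the pilot cited under Quantitative data analysis.
- Lowest primary care price considered: the £75 Band II fee.

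**Assumptions, because the protocol gives no value**
- Annual growth g: 0% to 20%.
- Primary care price c: £75 to £400.
- Annual programme cost P: £0, £20,000 or £50,000.

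**Implementation 1, P = £0**

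Raw saving = 650,000 × [1 − 0.91(1+g)]. Trend-adjusted saving = 650,000 × 0.09(1+g). Referrals avoided are these amounts divided by £650.

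| g | Raw saving | Adjusted saving | Avoided, raw | Avoided, adjusted |
|---|---|---|---|---|
| 0% | £58,500 | £58,500 | 90 | 90 |
| 5% | £28,925 | £61,425 | 44.5 | 94.5 |
| 10% | −£650 | £64,350 | −1 | 99 |
| 20% | −£59,800 | £70,200 | −92 | 108 |

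The raw saving reaches zero at g = 1/0.91 − 1 = 9.9%. With programme cost it does so at g = (1 − P/650,000)/0.91 − 1, which is 6.5% for P = £20,000 and 1.4% for P = £50,000.

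**Implementation 2, P = £0**

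Cost = 1,000(1+g)² × 0.91 × (0.32 × 650 + 0.68c). At g = 10% and c = £200 this is 1,101.1 × £344 = £378,778.
- Raw saving: 650,000 − 378,778 = £271,222.
- Adjusted saving: 1,210 × 650 − 378,778 = £407,722.

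The raw saving changes sign when (1+g)² × 0.91 × (208 + 0.68c)/650 = 1. That is g = 66% at c = £75, 44% at £200 and 22% at £400.

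**The ratio in implementation 1** (negative means a saving per referral avoided)
- Both parts raw, P = £0: −£650 at every g except the break-even point, because both parts scale together.
- Both parts raw, P = £20,000, g = 5%: −8,925/44.5 = −£201, against −41,425/94.5 = −£438 adjusted.
- Both parts raw, P = £50,000, g = 5%: 21,075/44.5 = +£474, against −11,425/94.5 = −£121 adjusted.
- Raw cost over trend-adjusted count, P = £0, g = 20%: 59,800/108 = +£554, against −£650.

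**Comparator years**

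Service costs are compared from months 1-12. Patient questionnaires are absent from the Phase 1 list. The baseline questionnaires mentioned under Screening and Selection of Subjects do not fill the gap: those participants are found through the referral management centre, which processes patients in implementations 1 and 2.

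**The case against.** The strongest counter-argument is that the text fixes only the cost numerator. The time-series estimate could supply the count of referrals avoided, and if both parts are raw and the programme costs nothing, the ratio is undistorted. This stands as a limit: the size of the error in the ratio depends on a definition the protocol does not give. It does not rescue the numerator, and a raw numerator over an adjusted count is one of the distorted cases above.

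The growth rate is also unknown for Sefton, the description of the rise is background, and the 9% covers all dental specialties in another area. That is fair; the figures show sensitivity and are not forecasts. Mean cost per patient, also planned, is free of volume growth, but it is a different measure.

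The alternative is imprecise too. For a straight line through 12 monthly points with independent errors of standard deviation σ, the projected year 3 monthly mean has standard error σ√(1/12 + 24²/143) = 2.03σ, against σ/√12 = 0.29σ for the baseline mean. If σ were 10% of the monthly mean (an assumption), two standard errors would be about 40%. One baseline year also holds only one seasonal cycle. This is a good reason to keep the raw difference beside the adjusted one.

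On patient costs, implementation 1 is a reasoned stand-in for care before diversion, since patients still attend their usual hospital clinic, and the sum is called only a proxy. That justifies the patient baseline but not adding it to an increment with another starting year.

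**Conclusion.** The point holds. The protocol prescribes a cost difference with no trend adjustment while describing a rising trend, so the saving is understated under any growth. In implementation 1 the shortfall is about half at 5% growth, and the sign is wrong above 9.9%, or at lower growth once programme cost is counted. In implementation 2 the saving is understated, with a reversal only at 22% to 66% annual growth, depending on the primary care price. All of this rests on the assumed ranges above and on the pilot effects.

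A reader might infer more than the documents support:
- **That year 3 would also show negative referrals avoided.** This follows only if diverted cases do not count as avoided. If they do, at 10% growth secondary care receives 1,210 × 0.91 × 0.32 = 352 referrals, so 648 are avoided on the raw count and 858 on the adjusted count.
- **That the ratio must be wrong.** It need not be, as the case with both parts raw and no programme cost shows.
- **That the economic result would contradict the primary analysis.** The primary analysis concerns referral number and destination; costs are a separate component.
- **That the unstated tariff price year is an error.** It may be set in an analysis plan that is not shown.

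The comparator mismatch in the societal figure is a separate, smaller point that follows from the text without any assumption about growth.

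**What to change.** 1. Define a referral avoided, including whether a case diverted to primary care counts.
2. Compute both costs and referrals avoided against the same trend-adjusted expectation for the same months: the interrupted time series projection, with a second version based on the planned HES national trend because 12 baseline months project poorly. Report both with intervals, alongside the raw difference.
3. Form the societal increment only for implementation 2 against implementation 1, where both cost types are measured, and keep the trend adjustment there; otherwise report the service and patient increments separately.

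This needs changed analysis wording and further analysis of data already planned, with no new collection. The main cost is wide intervals on the trend-adjusted figures, which may leave the implementation 1 saving unresolved. Restricting the societal figure to implementation 2 against 1 also means it says nothing about referral management without diversion.
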